12.1.4 Deaths

A table presenting the number and percentage of subjects who died during the Treatment Period will be presented for the Safety Analysis Set, respectively. Deaths occurring in the study will also be listed for all screened subjects, if death occurs within the study.

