At the EOS/ET Visit, the following procedures and assessments will be performed: urine pregnancy test for all female subjects who are of childbearing potential; evaluation of previous injection site for potential reaction and evidence of attempts to remove the depot; vital sign measurements; UDS; C-SSRS since last visit, counseling (manual-guided behavioral therapy); use of concomitant medications; assessment for AEs; brief physical exam; height and body weight measurement (to determine a subject’s body mass index [BMI]); hip and waist circumference measurement (to determine a subject’s hip-to-waist ratio); and laboratory tests (hematology, chemistry, urinalysis).

Approximately 4 weeks after EOS/ET Visit, all subjects should be contacted by telephone for a safety follow-up assessment of AEs and use of any concomitant medications.

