#### **6.9.4 Timing**

AEs will be captured from the time the subject gives informed consent until the subject completes the Safety Follow-Up Visit.

Surgical procedures, planned before enrollment of the subject in the study, are not considered AEs if the condition was known before study inclusion. In this case the medical condition should be reported in the subject's medical history (see Section 6.1).

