#### 9.5.1.1 Adverse Events

All AEs will be coded using the most up-to-date version of the Medical Dictionary for Regulatory Activities (MedDRA) and reported to the FDA. AEs that began after the EOS visit will not be included in the safety analysis. Only TEAEs occurring post administration of RBP-6000 will be included in the safety analysis (See [Section 6.9.2](#)).

The incidence of AEs (number and percent of subjects reporting the AE at least once during the study) will be summarized for all AEs, by the relationship to IMP and by severity.

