12.1.2 Serious Adverse Events

SAEs and treatment-related SAEs will be summarized separately by SOC and PT for the Safety Analysis Set.

All SAEs recorded on the CRF will be listed for all subjects.

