20.0 DATA HANDLING CONVENTIONS

20.1 REFERENCE DATES AND ANALYSIS PERIODS

There are two analysis periods in this study:

- Treatment Period (TP)
- Safety Follow-Up Period (SFU).

Treatment Period starts from Treatment Start Date and ends at Treatment End Date. Treatment Start Date (or Day 1) for a subject is the date of the first injection. Treatment End Date for a subject is the maximum of the date of the end-of-study/ Early Termination (EOS/ET) visit and the date of last injection + 28.

Safety Follow-Up Period starts from Safety Follow-Up Start Date and ends at Safety Follow-Up End Date, which are defined for all subject who have assessments in the Follow-Up period.

Safety Follow-Up Start Date for a subject is Treatment End Date +1.

Safety Follow-Up End Date for a subject is defined as the date of visit at Week 29 or unscheduled visit after the Treatment End Date (defined as above) for AE/concomitant medication reporting or lab/vital signs assessment, whichever comes later. That is, Follow-up end date is max (Follow-up Start Date, date of visit at Week 29, last unscheduled visit after the Treatment End Date to report AE/concomitant medication or to do lab/vital signs assessment, if available).

Any records collected prior to first injection date/time will be considered as Screening records. And any records collected after the Treatment End Date will be considered as Safety Follow-up records.

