14.3 Safety Data Tables & Figures

Table 14.3.1.1 Overall Summary of Treatment-Emergent Adverse Events – Safety Analysis Set
Table 14.3.1.2 Summary of Treatment-Emergent Adverse Events by MedDRA System Organ Class and Preferred Term During the Treatment Period – Safety Analysis Set
Table 14.3.1.3 Summary of Treatment-Emergent Adverse Events Experienced by >=5% of Subjects by MedDRA Preferred Term During Treatment Period– Safety Analysis Set

Table 14.3.14 Summary of Treatment-Emergent Adverse Events Leading to Discontinuation by MedDRA System Organ Class and Preferred Term During Treatment Period- Safety Analysis Set

Table 14.3.1.5 Summary of Deaths due to Adverse Event (AE) - Safety Analysis Set

Table 14.3.1.6 Summary of Serious Treatment-Emergent Adverse Events by MedDRA System Organ Class and Preferred Term During Treatment Period- Safety Analysis Set

Table 14.3.1.7 Summary of Serious Treatment-Emergent Adverse Events Related to Study Treatment by MedDRA System Organ Class and Preferred Term During Treatment Period- Safety Analysis Set

Table 14.3.1.8 Summary of Treatment-Emergent Adverse Events by Maximum Severity, MedDRA System Organ Class and Preferred Term During Treatment Period – Safety Analysis Set

Table 14.3.1.9 Summary of Treatment-Emergent Adverse Events Related to Study Treatment by Maximum Severity, MedDRA System Organ Class and Preferred Term During the Treatment Period- Safety Analysis Set

Table 14.3.1.10 Summary of Severe Treatment-Emergent Adverse Events Related to Study Treatment Leading to Discontinuation by MedDRA System Organ Class and Preferred Term During the Treatment Period- Safety Analysis Set

Table 14.3.1.11 Summary of Severe Treatment-Emergent Adverse Events by MedDRA System Organ Class and Preferred Term During the Treatment Period- Safety Analysis Set

Table 14.3.1.12 Summary of Treatment-Emergent Adverse Events Potentially Pertaining to Drug Withdrawal Symptoms by MedDRA System Organ Class and Preferred Term During the Treatment Period- Safety Analysis Set

Table 14.3.1.13 Summary of Treatment-emergent Adverse Events Potentially Pertaining to Drug Withdrawal Symptoms During the Safety Follow-up Period for Subjects Who Entered into the Safety Follow-up Period

Table 14.3.1.14 Summary of Treatment-Emergent Adverse Events Potentially Pertaining to Injection Site Reactions by MedDRA System Organ Class and Preferred Term During the Treatment Period- Safety Analysis Set

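### Deaths after the Treatment End Date, and SAEs starting after it, are collected and listed but enter no dedicated death or SAE count table, and SAP text and table titles disagree on the period covered

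*SAP*

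**What the plan says.** **Collection.** Protocol 6.9.4: "AEs will be captured from the time the subject gives informed consent until the subject completes the Safety Follow-Up Visit". Protocol Synopsis: "Approximately 4 weeks after EOS/ET Visit, all subjects should be contacted by telephone for a safety follow-up assessment of AEs". The Schedule of Events puts EOS at Day 169 and the follow-up contact at Day 197.

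**Periods.** SAP 20.1: "There are two analysis periods in this study", namely the Treatment Period and the Safety Follow-Up Period. The first ends on the Treatment End Date, the "maximum of the date of the end-of-study/ Early Termination (EOS/ET) visit and the date of last injection + 28" days; the second starts the next day. Under SAP 12.1.1 a newly arising event is a TEAE only if it starts before the Treatment End Date.

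**Deaths.** SAP 12.1.4: "A table presenting the number and percentage of subjects who died during the Treatment Period will be presented for the Safety Analysis Set". The title of Table 14.3.1.5 in Appendix 3 names no period. Deaths are also listed for all screened subjects (Listing 16.2.13).

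**SAEs.** SAP 12.1.2: "SAEs and treatment-related SAEs will be summarized separately by SOC and PT for the Safety Analysis Set", with no period limit. The title of Table 14.3.1.6 does have one: "Summary of Serious Treatment-Emergent Adverse Events by MedDRA System Organ Class and Preferred Term During Treatment Period- Safety Analysis Set". Table 14.3.1.7, for related events, has the same limit. All SAEs are listed (Listing 16.2.14).

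**Follow-up.** SAP 12.1.5 and Table 14.3.1.13 tabulate withdrawal-type events in the Safety Follow-Up Period. Protocol 9.5.1.1 says: "AEs that began after the EOS visit will not be included in the safety analysis".

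**The concern.** Safety monitoring is part of the study's only objective (Protocol section 2), and the follow-up contact exists to collect events after the last dosing interval. Protocol section 1 describes release over at least 28 days, so this contact covers the time when the depot is running down or exhausted. The plan tabulates withdrawal-type terms from this period but gives no count, denominator or percentage for deaths or SAEs. A report that follows SAP 12.1.4 literally could show a death table of zero although a subject died on study. It could also contradict itself, because the overall adverse event summary (SAP 12.1.1) counts fatal TEAEs by onset while the death table counts by date of death.

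**Working it through.** The plan gives no figure to reproduce: the sample size of about 300 has no derivation. The check compares the rules and then does day arithmetic.

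**Where each event goes (12.1.4 text and SAE table titles applied as written)**

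- Non-fatal SAE starting after the Treatment End Date: Listing 16.2.14, not Tables 14.3.1.6 or 14.3.1.7. If its preferred term is on the withdrawal list it also enters Table 14.3.1.13, not marked as serious.
- Fatal SAE starting after the Treatment End Date: Listings 16.2.13 and 16.2.14, not the death or SAE tables.
- TEAE starting in the Treatment Period, death after it: counted as a fatal TEAE in the overall summary, but not in the death table. One output shows 1 and the other 0.
- If the title of Table 14.3.1.5 governs instead of the 12.1.4 text, both deaths could be counted. The SAP does not say which governs.

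Table 14.3.1.13 has its own mismatch. Its title says treatment-emergent, yet an event that newly starts in follow-up cannot meet the SAP's TEAE definition. The text of 12.1.5, which says adverse events, is what makes the table workable.

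**Days affected**

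Inputs: injection 6 on Day 141, EOS on Day 169 and contact on Day 197 (Protocol Appendix 1); Treatment End Date rule (SAP 20.1).

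- On-schedule completer: 141 + 28 = 169, so the Treatment End Date is max(169, 169) = Day 169. Follow-up is 197 − 169 = 28 days, and 28/197 = 14.2%.
- General case: EOS/ET is k days after the last injection and the contact 28 days later. Follow-up days beyond the Treatment End Date = k + 28 − max(k, 28) = min(k, 28).
- k = 7 gives 7 days; 14 gives 14; 21 gives 21; 26 gives 26; 28 and 35 both give 28.

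**Subject-time**

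- Upper bound, all 300 subjects contributing 28 days: 300 × 28/365.25 = 23.0 subject-years.
- If 200 contributed 28 days and the rest none (an assumption): 200 × 28/365.25 = 15.3 subject-years.

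**Illustration only; no rate is given in the documents**

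Chance of at least one death missing from the death table = 1 − exp(−rate × subject-years):

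| Assumed deaths per 100 subject-years | 23.0 subject-years | 15.3 subject-years |
|---|---|---|
| 1 | 21% | 14% |
| 2 | 37% | 26% |
| 3 | 50% | 37% |

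For SAEs and deaths together, at assumed per-subject risks of 0.1%, 0.5% and 1% in the uncounted window, 1 − (1 − p)^300 = 26%, 78% and 95%.

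**The case against.** The strongest reply is that nothing is lost. Every death and SAE is listed for all subjects, and at the assumed death rates the expected number of follow-up deaths is at most about 0.2 to 0.7 (23.0 × 0.01 to 23.0 × 0.03), which a listing shows in full. The cut-off was also pre-specified: Protocol 9.5.1.1 excludes events that begin after EOS. The SAP's Treatment Period is, if anything, wider, since it runs to at least 28 days after the last injection and so spans the approximate release period in Protocol 5.2. SAP 12.1.2 sets no limit, and SAP 12.0 says analyses are done by analysis period, of which there are two. In a single-group descriptive study there is no comparison to bias.

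Much of this stands. A reader might infer that follow-up events enter no summary table at all, or are concealed. The documents do not support either: Table 14.3.1.13, the fatal-TEAE line and the listings each capture some or all of them. A reader might also infer that the SAP settles on exclusion; 12.1.2 and the title of Table 14.3.1.5 show that it does not.

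What does not stand is the conclusion that no change is needed. A listing gives no count or percentage. No follow-up SAE table is planned despite the general wording of 12.0. The SAP already departs from Protocol 9.5.1.1 by tabulating withdrawal-type events in follow-up, so the protocol exclusion does not explain why deaths and SAEs are treated differently.

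**Conclusion.** The point holds in a limited form. Under the 12.1.4 text and the titles of Tables 14.3.1.6 and 14.3.1.7, the dedicated counts omit on-study deaths after the Treatment End Date and SAEs that start after it. The inconsistency between text and titles is certain and depends on no assumption.

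The affected time is all 28 follow-up days for a subject whose EOS/ET visit is 28 or more days after the last injection, and min(k, 28) days otherwise. It would be wrong to read 23 subject-years as the expected amount. That figure requires every subject to reach EOS on schedule and complete follow-up, whereas subjects may stop at any time and losses to follow-up are foreseen. The probabilities rest wholly on assumed rates and are not estimates for this trial. The change should be made because it affects the tabulated counts for the study's stated objective, but no comparison or hypothesis test depends on it.

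**What to change.** In SAP 12.1.2 and 12.1.4 and in Tables 14.3.1.5 to 14.3.1.7:

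- Keep the Treatment Period column.
- Add a Safety Follow-Up Period column and a total from first dose to end of follow-up, stating the denominator of each.
- Classify deaths by date of death and SAEs by date of onset, and say so in a footnote so that the death table can be reconciled with the fatal-TEAE line.
- Make the section text and the table titles state the same periods.
- Record the departure from Protocol 9.5.1.1 in SAP section 21, which now says that nothing was changed. Protocol 9.1 provides for the SAP to carry such deviations, so a protocol amendment is not shown to be necessary.

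The cost is extra columns in three tables, from data already collected. The tabulated totals may be slightly less favourable.

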12.1.5 Potentially Pertaining to Drug Withdrawal Symptoms

A summary of TEAEs potentially pertaining to drug withdrawal during the Treatment Period, as defined in [Appendix 1](#), will be summarized by SOC and PT for the Safety Analysis Set.

Additionally, A summary table of Adverse Events potentially pertaining to drug withdrawal during the Safety Follow-up Period will be used to tabulate AEs related to drug withdrawal symptoms in the Safety Follow-Up period after EOS/ET visit, if any.

12.1.6 Potentially Pertaining to Injection Site Reactions

A summary of TEAEs potentially pertaining to injection site reactions, as defined in Appendix 1, will be summarized by SOC and PT for the Safety Analysis Set.

12.1.7 Hepatic Disorders Topic of Special Interest

A summary of TEAEs potentially related to hepatic disorders, as defined in Appendix 1, will be summarized by SOC and PT for the Safety Analysis Set.

12.1.8 Central Nervous System Depression Topic of Special Interest

A summary of TEAEs related to Central Nervous System Depression, as defined in Appendix 1, will be summarized by SOC and PT for the Safety Analysis Set.

12.1.9 Respiratory Depression Topic of Special Interest

A summary of TEAEs related to respiratory depression, as defined in Appendix 1, will be summarized by SOC and PT for the Safety Analysis Set.

12.1.10 Acute Pancreatitis Topic of Special Interest

A summary of TEAEs related to acute pancreatitis as defined in Appendix 1, will be summarized by SOC and PT for the Safety Analysis Set.

12.1.11 Orthostatic Hypotension Topic of Special Interest

A summary of TEAEs related to orthostatic hypotension, as defined in [Appendix 1](#), will be summarized by SOC and PT for the Safety Analysis Set.

12.1.12 Psychiatry History Topic of Special Interest

A summary of TEAEs regarding psychiatry history, as defined in Appendix 1, will be summarized by SOC and PT for the Safety Analysis Set.

12.2 CLINICAL LABORATORY PARAMETERS

Laboratory data will be reported using International System (SI) units (and using original units for some parameters if necessary) as collected by the central laboratory. Unless otherwise specified, all continuous laboratory data will be summarized using descriptive statistics (n, mean, SD, median, min and max) for each scheduled study assessment as well as change from baseline and percentage change from baseline [if applicable] by parameter class (hematology, chemistry, and urinalysis). All laboratory assessments include a baseline summary as defined in Section 20.2 unless otherwise indicated. Hematology chemistry and urinalysis data will be summarized by displaying shifts from baseline value to EOS/ET visit. All laboratory assessments will be listed by panel with the corresponding normal ranges for each parameter. Screening laboratory tests will also be listed.

The peak total bilirubin [x ULN] vs. peak aspartate aminotransferase (or peak alanine aminotransferase) [x ULN] on a log/log scale during the Treatment Period will be plotted in the Safety Analysis Set. And the box plot to access clinical liver safety data by maximum change from baseline during the Treatment Period will be plotted for lab tests ALT, AST and total bilirubin.

Summary of potential hepatotoxicity for serum chemistry by type of criterion (shown in Table 5) and by analysis visit and at any time post baseline will be tabulated for the Safety Analysis Set. For “Any time post baseline”, a subject will be classified to their highest/worst applicable toxicity grade per criterion, among the post baseline visits including unscheduled visits, and be counted only once in the category corresponding to the worst grade. For subjects who met the criteria for potential hepatotoxicity (any time post baseline), their test results for ALT, AST, TBIL, ALP during study (i.e., at all scheduled and unscheduled visit) will be provided in a listing.

Table 5: Criteria for Potential Hepatotoxicity Laboratory Value

Criteria
ALT > 3 x ULN to < 5 x ULN
ALT \geq 5 x ULN to < 8 x ULN
ALT \geq 8 x ULN
AST > 3 x ULN to < 5 x ULN
AST \geq 5 x ULN to < 8 x ULN
AST \geq 8 x ULN
ALT & AST > 3 x ULN to < 5 x ULN
ALT & AST \geq 5 x ULN to < 8 x ULN
ALT & AST \geq 8 x ULN
TBIL > 2 x ULN to < 5 x ULN
TBIL \geq 5 x ULN
HYs Law: (all must be met to meet Potential Hy's law)
ALT or AST > 3 x ULN
TBIL > 2 x ULN
ULN < Alkaline phosphatase (ALP) < 2xULN

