Subjects will not be permitted to receive supplemental buprenorphine during the RBP-6000 treatment period (Day 1 to EOS/ET Visit). Subjects who require supplemental buprenorphine pharmacotherapy during the RBP-6000 treatment period will be withdrawn from the study and referred for appropriate treatment. [Note: If subjects complete their EOS/ET Visit and a new treatment venue for them has not been identified, the Investigator may provide the subject further buprenorphine treatment or another appropriate treatment according to their own medical judgement.]

Subjects will return to the site for monthly injection visits every 28 days (-2 / +7 days) for a total of up to 6 injections. Subjects are not required to complete all 6 injections and may choose to “early terminate” (ET) the study at any time.

At each subsequent visit (Injection Visits 2 through 6) the following procedures and assessments will be performed: urine pregnancy test for all female subjects who are of childbearing potential before each injection; evaluation of previous injection site for potential reaction and evidence of attempts to remove the depot; collection of vital signs pre- and post-injection; RBP-6000 injection; urine drug screen (UDS); C-SSRS since last visit assessment, counseling (manual-

guided behavioral therapy); local injection site grading; subject self-assessment of injection site pain (Injection site Pain VAS); use of concomitant medications; and assessment for AEs.

Laboratory tests (hematology, chemistry and urinalysis) may be requested by the Investigator on an ad-hoc basis as necessary to further examine any AEs.

[figure not shown]
Alternative treatment options should be assessed at least two months before EOS at each visit, however it is recommended where possible to assess at every visit.

At the EOS/ET Visit, the following procedures and assessments will be performed: urine pregnancy test for all female subjects who are of childbearing potential; evaluation of previous injection site for potential reaction and evidence of attempts to remove the depot; vital sign measurements; UDS; C-SSRS “since last visit” assessment, counseling (manual-guided behavioral therapy); use of concomitant medications; assessment for AEs; brief physical exam; height and body weight measurement (to determine a subject’s BMI); hip and waist circumference (to determine a subject’s hip-to-waist ratio); and laboratory tests (hematology, chemistry, urinalysis).

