20.2 ANALYSIS VISITS AND OTHER DEFINITIONS

All data will be presented in listings (including unscheduled visits), however only per-protocol visits will be summarized in tables and figures. Unscheduled and scheduled assessments will be utilized in the summaries for “at any time”.

For lab values, body weight, BMI, waist circumference, hip circumference and waist-to-hip ratio, Early Termination and End-of-study results will be reported with the EOS/ET visit.

For all other assessments, occurring at the ET visit, will be mapped to the next per-protocol visit (or time point), that has not already been completed by the subject. A ET visit must not be mapped to a visit that a subject has already completed.

The closest assessment value on or before Treatment Start Date/Time will be assigned as Baseline value and then be labeled as 'Baseline' in visit window, and for assessment prior to Treatment Start Date/Time, if exists, will be labeled as 'EOS 0003' or 'Screening' per its collecting time and per SOE definition.

For subjects who have one visit-based assessment in the Safety Follow-up (SFU) period, the period of the visit will be labeled as 'Safety Follow-Up Week 29'.

Other Definitions:

Subgroups

Sex

- Male
- Female

Age Categories

- ≥ 18 to < 30
- ≥ 30 to < 45
- ≥ 45 to < 60
- ≥ 60
- ≥ 65

Race

- White
- Non-White

Baseline BMI Categories

- Under weight: 0 to $< 18.5 \text{ kg/m}^2$
- Normal: $\geq 18.5 \text{ kg/m}^2$ and $< 25 \text{ kg/m}^2$
- Over weight: $\geq 25 \text{ kg/m}^2$ and $< 30 \text{ kg/m}^2$
- Obese: $\geq 30 \text{ kg/m}^2$

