20.4 REPEATED OR UNSCHEDULED ASSESSMENTS OF SAFETY PARAMETERS

See reference rules on unscheduled assessments in [Section 20.2](#). Unscheduled assessments will be utilized in analyses “at any time” and will be listed in listings.

If there are more one assessments on one parameter at scheduled visits, the last assessment will be used for visit-based table/figure summaries.

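### Apart from the liver displays, laboratory tables use only baseline and EOS/ET, so a transient abnormality seen in an unscheduled sample is tabulated as no shift

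*SAP*

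**What the plan says.** **Sampling.** Protocol 9.5.1.2 and the Schedule of Events (Appendix 1) place hematology, chemistry and urinalysis at two points: the prior study's EOS visit, which serves as screening on Day 1, and EOS/ET (Day 169). Between them, Protocol 3.1 says that these tests "may be requested by the Investigator on an ad-hoc basis as necessary to further examine any AEs".

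**Tabulation.** SAP 12.2 summarizes continuous laboratory values at scheduled assessments and defines the shift tables thus: "Hematology chemistry and urinalysis data will be summarized by displaying shifts from baseline value to EOS/ET visit". SAP 20.2 sets the general rule: "All data will be presented in listings (including unscheduled visits), however only per-protocol visits will be summarized in tables and figures". The exception follows: "Unscheduled and scheduled assessments will be utilized in the summaries for" results at any time. SAP 20.4 repeats it.

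**Where the exception is used.** SAP 12.2 uses it for the hepatotoxicity criteria of its Table 5: "a subject will be classified to their highest/worst applicable toxicity grade per criterion, among the post baseline visits including unscheduled visits". It also plans plots of peak total bilirubin against peak AST or ALT, and a box plot of maximum change for ALT, AST and total bilirubin. The table list in SAP Appendix 3 has no worst-value version of the by-visit tables (14.3.5.1 to 14.3.5.3) or of the shift tables (14.3.5.5 to 14.3.5.7).

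**The concern.** Safety monitoring is part of the study's single objective, and SAP 12.0 names changes in laboratory results among its three lead safety variables. The analysis is wholly descriptive, so the tables are the result that most readers will see.

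Under these rules, the samples drawn because something was wrong are the ones that the non-hepatic tables omit. Protocol 6.5.1 adds to this. A clinically significant abnormality is repeated until it resolves or until resolution is not expected. A mid-study abnormality that is followed to recovery therefore leaves several unscheduled records and a normal EOS/ET value.

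For liver tests the SAP already counts the worst value, unscheduled samples included. It gives no reason for stopping there.

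**Working it through.** The documents state no figure to reproduce. The check applies the SAP's rules to one subject and then looks at scale.

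**Step 1: which samples count.** The scheduled samples are baseline (Day 1) and EOS/ET (Day 169). The interval is 169 − 1 = 168 days, or 24 weeks, with no scheduled hematology, chemistry or urinalysis.

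**Step 2: a test subject**, for a parameter such as creatinine.

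| Record | Type | Category |
|---|---|---|
| Baseline | scheduled | Normal |
| Mid-study, taken for an AE | unscheduled | High |
| EOS/ET | scheduled | Normal |

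- SAP 12.2 with 20.2: the unscheduled record is dropped, and the result is Normal to Normal (no shift).
- Worst post-baseline value, unscheduled samples included: Normal to High.

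The by-visit tables also omit the High value. It appears in the relevant one of Listings 16.2.26 to 16.2.28, and in the AE tables if it is recorded as a treatment-emergent AE.

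**Step 3: limits of the example.** The result of no shift requires baseline and EOS/ET values in the same category. A subject with no EOS/ET sample is missing from the shift instead. SAP 20.4 takes the last of several assessments at a scheduled visit, so an abnormal EOS/ET value with a normal repeat recorded under that visit is also tabulated as normal.

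**Step 4: scale, on assumed rates only.** Let q be the proportion of subjects who have a non-hepatic abnormality that was caught in an unscheduled sample and had returned to the baseline category by EOS/ET. The documents do not give q. With n = 300 (the approximate planned enrolment), the expected number is 300q, and the probability of at least one is 1 − (1 − q)^300.

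| Assumed q | Expected subjects | P(at least one) |
|---|---|---|
| 0.5% | 1.5 | 0.778 |
| 1% | 3 | 0.951 |
| 2% | 6 | 0.998 |
| 5% | 15 | above 0.999 |

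Ad hoc testing is optional, so q could also be close to zero.

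**The case against.** The strongest reply is that the safety signal is handled elsewhere, and much of that stands.

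- **AE tables.** The AE that prompted the sample is already recorded. Under Protocol 6.5.1, a clinically significant abnormality becomes an AE itself unless it is considered erroneous. Protocol 6.9.1 adds abnormalities that lead to treatment, further diagnostic evaluation or discontinuation.
- **Listings.** All values, unscheduled ones included, are listed with normal ranges. A reader might infer that the values are lost. They are not.
- **Lipase and amylase.** A reader might infer that the pancreatitis markers go unsummarized. SAP 12.1.10 plans "A summary of TEAEs related to acute pancreatitis as defined in Appendix 1", and that list contains amylase increased, lipase increased and hyperlipasaemia, which feed Table 14.3.1.15. These enzymes are weaker examples than creatinine, creatine kinase, electrolytes or blood counts, around which the SAP builds no topic list.
- **Withdrawals.** Protocol 3.3 requires an EOS/ET visit of dosed subjects who discontinue, and SAP 20.2 reports ET laboratory results under EOS/ET. A toxicity that ends participation can therefore still appear in the shift table if the visit is attended.
- **No contradiction.** Protocol 9.5.1.2 promises only summaries at screening and EOS with change from baseline. The SAP meets this and adds to it.

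The AE tables are still not a full substitute. Under Protocol 6.9.9, laboratory changes are reportable only if the investigator judges them clinically significant, and the study is open-label. A shift table applies the reference range without that judgment. What lacks any table is the sampled, out-of-range, recovered value that was not judged to be an AE. An abnormality that was recorded as an AE is counted there but still shows as no shift.

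**Conclusion.** The concern holds as a limited gap in the tables. Outside the hepatic displays, a transient abnormality found only in an unscheduled sample and recovered by EOS/ET is tabulated as no shift. This follows directly from SAP 12.2, 20.2 and 20.4 and the two-point laboratory schedule. It needs no assumption beyond the subject having both a baseline and an EOS/ET value.

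The size is unknown. The 1.5 to 15 subjects above rest on assumed rates and on a sample of about 300, and are not an estimate for this trial.

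Two stronger readings are tempting and not supported. One is that the tables omit the values most likely to reflect drug toxicity; the documents give no evidence on which values those are. The other is that better tables would recover every abnormality that resolves before EOS/ET. They could recover only those that were sampled. An improvement worth making, but not one on which the study's conclusions depend.

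**What to change.** Add to SAP 12.2 and to the shells in Appendix 3:

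- **Tables 14.3.5.5 and 14.3.5.6 (hematology, chemistry).** Beside the EOS/ET shift, show a shift from baseline to the worst value, labelled as any time post baseline so that it falls under the existing SAP 20.2 exception. Use scheduled and unscheduled samples, and give the low and high directions separately.
- **Exclusions.** SAP 20.9 merges categories, so there is no low direction for LDH, total bilirubin, AST or GGT, and no high direction for HDL-C. SAP 12.2.1 has platelets at EOS/ET only, so they have no baseline shift.
- **Table 14.3.5.7 (urinalysis).** Use normal to abnormal, and only for parameters with a reference category. Low and high mean nothing for color or appearance.
- **Context in each table.** Show the number of subjects with any unscheduled sample. Footnote that unscheduled sampling is AE-driven, and that the new columns supplement the EOS/ET shift and do not replace it.

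The cost is SAP wording and one extra column block from data already collected, with no protocol amendment. The downside is that its percentages reflect unequal sampling between subjects, in a single-arm study with no comparator.
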